6.3 E-DBTP Efficacy Analysis Set

The E-DBTP efficacy analysis set consists of a subset of subjects from full analysis set who receive week 12 dose. Subjects will be analyzed according to their randomized treatment, regardless of treatment received. Analysis of exploratory efficacy endpoints during E-DBTP will utilize this efficacy analysis set.

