8.1.4 Treatment Period

Visits will occur per the Schedule of Activities (Table 1-1). The date of the first dose of investigational product is defined as day 1. All subsequent doses and study visits will be scheduled based on the day 1 date. Study visits after day 1 may be completed within ± 3 days of the scheduled visit. All study procedures for a given study visit are to be completed on the same day. Investigational product is to be administered Q4W as the last procedure during each visit that it is required.

Subjects who discontinue investigational product are encouraged to remain in the study and complete all remaining procedures and study visits.

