9.3.1.2 Efficacy Analysis Set

The respective efficacy analysis set consists of a subset of subjects from full analysis set who receive at least 1 dose of investigational product and have a baseline value and at least 1 post baseline value for the endpoint of interest. Subjects will be analyzed according to their randomized treatment, regardless of the treatment received. Primary analysis of the efficacy endpoints will utilize the respective efficacy analysis set.

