9.4.2 Methods of Analyses

9.4.2.1 General Considerations

Summary statistics will be computed by treatment group and visit. For continuous endpoints, the following descriptive statistics will be computed: number of observations, means, medians, standard deviations, standard errors, first and third quartiles, minimums and maximums, and 2-sided 95% CIs of the means (CIs will be provided for efficacy endpoints only). For categorical endpoints, the summaries will contain the number and percentage of subjects in each category.

The primary analysis method utilizing a repeated measures linear mixed effects model will include all observed data regardless of treatment adherence.

A sequential testing procedure will be used to maintain the family-wise type 1 error $\alpha = 0.05$ between the primary and secondary endpoints following the prespecified order below. An endpoint will only be tested for statistical significance if the endpoint tested in the previous step is statistically significant at 2-sided significance level of 0.05.

1. Primary endpoint: change from baseline in mean monthly hours of at least moderate headache pain intensity over months 1, 2, and 3

- 2. Secondary endpoints: change from baseline in mean monthly function domain score over months 1, 2, and 3, as measured by the MFIQ using the Hochberg procedure
 - Impact on physical functioning
 - Impact on usual activities
 - Impact on emotional functioning
 - Impact on social functioning
- Secondary endpoint: change from baseline in mean monthly average duration of at least moderate pain intensity in migraine attacks occuring over months 1, 2, and 3 (migraine attacks as defined in Section 11.1)
- 4. Secondary endpoint: change from baseline in mean monthly average peak migraine pain intensity over months 1, 2, and 3, as assessed by the 11-point NRS

Endpoint	Statistical Analysis Methods
Primary	The primary endpoint will be analyzed using a linear mixed effects model including treatment group, baseline value, scheduled visit, and the interaction of treatment group with scheduled visit, without any imputation for missing data.
Secondary	The secondary endpoints will be analyzed using a linear mixed effects model including treatment group, baseline value, scheduled visit, and the interaction of treatment group with scheduled visit, without any imputation for missing data.
Exploratory	Detailed primary analysis method for exploratory endpoints will be described in the SAP.

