9.5 Efficacy Analyses

The primary and secondary efficacy analyses will utilize the M-DBTP EAS and the exploratory efficacy analyses will utilize the E-DBTP EAS. Subjects will be analyzed according to their randomized treatment group regardless of the actual treatment received during the study.

Detailed efficacy analysis methods and covariates included in the models are summarized in the table below.

Endpoint	Primary Summary and Analysis Method
Change from baseline in mean monthly hours of at least moderate headache pain intensity over months 1, 2, and 3	 Summary statistics by visit using observed data at each visit and the calculated mean monthly hours of headache pain over months 1, 2, and 3
	2. Least squares means from a linear mixed effect model including treatment group, scheduled visit, interaction of treatment and scheduled visit and baseline value using observed data
	 Estimate treatment difference (AMG 334 – Placebo) from the model in #2.

Table 9-1. Primary Efficacy Endpoint Summary Table

Table 9-2. Secondary Efficacy Endpoint Summary Table

Т

Endpoint	Primary Summary and Analysis Method
Change from baseline in mean monthly function as measured by the Migraine Functional Impact Questionnaire (MFIQ) over months	 Summary statistics by visit using observed data at each visit, and the calculated mean monthly values over months 1, 2 and 3
1, 2, and 3; Change from baseline in mean	 Least squares means from a linear mixed effect model including treatment group, scheduled visit, interaction of treatment and scheduled visit and baseline value using observed data
monthly average duration of at least moderate pain intensity in migraine attack s over months 1, 2, and 3;	 Estimate treatment difference (AMG 334 – Placebo) from the model in #2
Change from baseline in mean monthly peak migraine pain intensity as assessed by the 11-point Numeric Rating Scale (NRS) over months 1, 2, and 3	

Endpoint	Primary Summary and Analysis Method
Change from baseline in mean MMD over months 1, 2, and 3 ^a	 Summary statistics by visit using observed data at each visit and the calculated mean monthly migraine day over months 1, 2, and 3 Least squares means from a linear mixed effect model including treatment group, scheduled visit, interaction of treatment and scheduled visit and baseline value using observed data Estimate treatment difference (AMG 334 – Placebo) from the model in #2.

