Change from baseline in pain catastrophizing as measured by the Pain Catastrophizing Scale (PCS) at month 3 ^b	 Summary statistics using observed data at week 12 Analysis of covariance (ANCOVA) model including treatment group and baseline value using observed data Estimate treatment difference (AMG 334 – Placebo) using the model in #2.
Achievement of no or mild interictal burden as measured by the MIBS-4 at assessment time points ^c	 Summary statistics using observed data at the specific month Logistic regression model including treatment group and baseline value will be used after subjects with missing outcome data are imputed as non-responders (NRI)

Table 9-3. Exploratory Efficacy Endpoint Summary Table

Endpoint	Primary Summary and Analysis Method	
Achievement of pain freedom at 2 hours post-triptan dose for the first attack at month 4 ^d	Summary sta assessment f	itistics using observed data at the time points
	group will be	ession model including treatment used after subjects with missing ment are imputed as non-responders
Use of migraine rescue medication within 24 hours post-triptan dose for the first attack at month 4	Summary sta assessment	atistics using observed data at the time points
		ression model including treatment observed data
^a The same analyses methods will be applie	the endpoints:	

The same analyses methods will be applied to the endpoints:

Change from baseline in mean monthly hours of at least moderate pain intensity for qualifying oral triptan-treated migraine attacks over months 1, 2, and 3

Change from baseline in mean average duration of at least moderate pain intensity for qualifying oral triptan-treated migraine attacks occurring over months 1, 2, and 3

Change from baseline in Migraine Symptom Severity Score (MSSS) total score at assessment time points Change from baseline in mean monthly total migraine freedom days over months 1, 2, and 3

Change from baseline in Migraine Interictal Burden Scale (MIBS-4) total score at assessment time points (the model will include data at month 1-4)

Change from baseline in headache impact scores as measured by the Headache Impact Test (HIT-6) total score at assessment time points

Change from baseline in physical function domain score as measured by MFIQ at assessment time points Change from baseline in usual activities domain score as measured by MFIQ at assessment time points

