9.5.3 E-DBTP Analyses of Exploratory Efficacy Endpoints

The dichotomous efficacy endpoints for assessing qualifying triptan-treated attacks only in E-DBTP will be analyzed using logistic regression model with missing data imputed as non-responders (NRI) **up to End of Study Date**. Odds ratios of treatment group and placebo with associated 95% CIs and p-values will be reported. The efficacy endpoint for Migraine Interictal Burden Scale at month 4 will be analyzed using the linear mixed effects model that includes treatment group, baseline values, scheduled visit, and the interaction of treatment and scheduled visit without any imputation for missing data.

The following exploratory endpoints of the E-DBTP for the first qualifying triptan-treated attack will be analyzed by medication overuse status at month 3 (yes vs. no):

- Achievement of pain freedom at 2 hours post-triptan dose for the first attack at month 4
- Achievement of pain relief at 2 hours post-triptan dose for the first attack at month 4
- Achievement of relief from the most bothersome symptom at 30, 60, and 120 minutes post-triptan dose for the first attack at month 4
- Achievement of 24-hour sustained pain freedom post-triptan dose for the first attack at month 4
- Migraine recurrence within 24 hours post-triptan dose for the first attack at month 4
- Use of migraine rescue medication within 24 hours post-triptan dose for the first attack at month 4

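### The exploratory month-4 MIBS-4 comparison is limited to subjects who received the week 12 dose, a post-randomisation condition that this endpoint does not need

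*SAP*

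**What the plan says.** SAP 6.3 defines the set: "The E-DBTP efficacy analysis set consists of a subset of subjects from full analysis set who receive week 12 dose". It then assigns the set's use: "Analysis of exploratory efficacy endpoints during E-DBTP will utilize this efficacy analysis set". SAP 9.5 repeats the assignment without limiting it to month 4: "the exploratory efficacy analyses will utilize the E-DBTP EAS". SAP 9.5.3, which covers the E-DBTP analyses, includes the endpoint at issue: "The efficacy endpoint for Migraine Interictal Burden Scale at month 4 will be analyzed using the linear mixed effects model".

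Table 9-3, footnote a, also lists the MIBS-4 change endpoint, with this wording: "total score at assessment time points (the model will include data at month 1-4". The footnote names no analysis set. SAP 6.2 gives a separate set for endpoints of the main treatment phase.

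Protocol 9.3.1.2 had a single rule for efficacy endpoints: a randomised subject qualified with one dose or more, together with a baseline and a later value of the endpoint concerned. SAP section 10 declares the replacement of that set by two sets, giving as its reason only the target population of the endpoints.

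On follow-up after stopping treatment, Protocol 8.1.4 says: "Subjects who discontinue investigational product are encouraged to remain in the study and complete all remaining procedures and study visits". Protocol 7.1 likewise asks that such subjects stay on study so that outcome data can be collected.

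**The concern.** Whether a subject receives the week 12 dose can depend on how well the assigned treatment has worked and been tolerated over the preceding 12 weeks. Groups formed on that condition are no longer the randomised groups. The contrast then describes subjects who were still being dosed at week 12, whereas the stated objective is the treatment benefit on interictal burden, with no such restriction.

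For the triptan-attack endpoints the condition has a reason: SAP 5.4.2 starts their interval at the week 12 dose date. MIBS-4 is a visit questionnaire and has no such link. The rule removes permanent discontinuers and also anyone who merely missed that one dose. If the months 1 to 4 model is fitted on the same set, their scores from weeks 4, 8 and 12 go as well, and those scores are what would make a missing-at-random analysis more credible.

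**Working it through.** **1. Does MIBS-4 need the week 12 dose?** The Schedule of Activities and SAP 5.1.3 schedule it at day 1 and weeks 4, 8, 12 and 16. SAP Table 5-3 sets the month-4 target at study day 113 and the window at days 100 to 127, counted from the first dose. Neither refers to the week 12 dose.

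**2. Can a subject without that dose have a month-4 score?** The protocol gives two answers.
- Under 8.1.4, a subject who stops product completes the remaining visits, so a week 16 score falls near day 113, inside the window.
- Under 8.1.5, a subject who stops treatment or leaves the study before week 12 has the week 12 assessments as an early termination visit. For subjects leaving the study, the end-of-study visit is 4 weeks after the last dose. The latest possible last dose without a week 12 dose is week 8, target day 57. That gives 57 + 28 = day 85, or 60 + 28 + 3 = day 91 with both 3-day allowances used. This is in the week 12 window (days 72 to 99), not the month-4 window.

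The number of affected week 16 scores therefore depends on which passage sites follow, and could be zero.

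**3. The plan's own figure.** No effect, SD or power is given for MIBS-4. The primary power reproduces: with 288 × 0.9 ≈ 259 per arm, difference 16.7 and SD 50, the standardised difference is 16.7 / (50 × √(2/259)) = 3.80, and power is Φ(3.80 − 1.96) = 96.7%, against 96% stated. This shows only that the 10% is an allowance for study dropout. It is not a rate of stopping treatment before week 12.

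**4. Scores excluded (assumed inputs).** Let d be the share without a week 12 dose and r the share of those followed to week 16. Excluded week 16 scores = 576 × d × r.

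| d | per arm (288 × d) | r = 25% | r = 50% | r = 75% |
|---|---|---|---|---|
| 5% | 14 | 7 | 14 | 22 |
| 10% | 29 | 14 | 29 | 43 |
| 15% | 43 | 22 | 43 | 65 |

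**5. Shift in the contrast (assumed inputs).** Negative change is improvement. Let g be how many points worse the change is in non-dosed than in dosed subjects of the same arm. An arm's full mean is its dosed mean + d × g. Restricting to dosed subjects therefore moves erenumab minus placebo by d_P × g_P − d_E × g_E, on a scale of 0 to 12.

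| d_E, d_P | g_E, g_P | Shift (points) |
|---|---|---|
| 10%, 10% | equal, 1 to 3 | 0 |
| 10%, 10% | 1, 3 | +0.20 |
| 8%, 12% | equal, 1 to 3 | +0.04 to +0.12 |
| 5%, 15% | equal, 1 to 3 | +0.10 to +0.30 |
| 5%, 15% | 1, 3 | +0.40 |

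Positive values go against erenumab. Swapping the arms' inputs reverses the sign. These are comparisons with a week 16 score known for everyone; the fix can recover only the part due to subjects who stay on study.

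**6. Which population does footnote a use?** SAP 6.2 points main-phase endpoints to the M-DBTP set, while 9.5 sends exploratory analyses to the E-DBTP set. The footnote chooses neither, so the same month-4 contrast can be produced from two populations.

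**The case against.** The split into two sets is prespecified and openly declared in SAP section 10, for an exploratory phase. That stands as disclosure, but the stated reason does not explain why a dosing condition suits a questionnaire, and no passage says that an on-treatment question is intended.

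A reader might infer that the protocol requires all data for this endpoint, since Protocol 9.4.2.1 says: "The primary analysis method utilizing a repeated measures linear mixed effects model will include all observed data regardless of treatment adherence". The documents do not support going that far. The same section leaves exploratory methods to the SAP, and SAP 9.1 limits the equivalent sentence to primary and secondary endpoints. The firmer anchor is the analysis set of Protocol 9.3.1.2.

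Footnote a, if run on the M-DBTP set, may already give a month-4 contrast that includes non-dosed subjects. That is possible, but it leaves the rule in 6.3 and 9.5.3 in place and adds a second version of the result.

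Few week 16 scores may exist outside the set, because of Protocol 8.1.5. That stands and limits what can be recovered. The Protocol 9.3.1.2 set also conditions on a post-randomisation event, a post-baseline value; this too is true, but the condition is much weaker than being dosed at week 12.

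**Conclusion.** The restriction is unsuited to month-4 MIBS-4 and should be removed for that endpoint. Any bias may go in either direction. Its size cannot be derived from the documents: every loss share, follow-up share and gap used above is an assumption, and the number of week 16 scores affected is unknown.

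A reader might infer that the result overstates the benefit by 11%, from 1/(1 − 0.10), and that about 58 of 576 subjects lose all their MIBS-4 data. The documents do not support either figure. Both take the 10% study-dropout allowance as treatment stopped before week 12. The first also assumes equal loss in the arms and no month-4 benefit in those who stop. Subjects who leave the study have no week 16 score to recover. The second figure holds only if every MIBS-4 analysis uses the 6.3 set, which the SAP leaves unclear.

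The endpoint is exploratory, unpowered and outside the testing sequence. Type I error control and the primary and secondary conclusions are unaffected; what is at stake is the interpretation of the month-4 interictal result.

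**What to change.** - In SAP 6.3, 9.5.3 and Table 9-3 footnote a, state that month-4 MIBS-4 is analysed in all randomised subjects with at least one dose, a baseline MIBS-4 and at least one post-baseline MIBS-4 (the Protocol 9.3.1.2 set). Use all observed scores in the single months 1 to 4 mixed model and report the month-4 contrast from that model only.
- Keep the week-12-dose set for the episode-diary attack endpoints and, if wanted, for a supplementary MIBS-4 analysis labelled as such.
- Reconcile Protocol 8.1.4 and 8.1.5 on which visits follow when treatment stops before week 12, and tabulate by arm how many subjects without a week 12 dose have a score in days 100 to 127.

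The analysis change is SAP wording, to be settled before unblinding, and uses scores already on the schedule. The month-4 estimate may become less favourable, and subjects who leave the study will still rely on the missing-at-random assumption, though with their earlier scores in the model.

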6.4 Safety Analysis Set

The safety analysis set will consist of all randomized subjects who receive at least 1 dose of investigational product. Subjects will be analyzed according to the randomized treatment unless a subject has received the incorrect dose during the entire DBTP, in which case, the subject will be analyzed according to the actual treatment received.

Analysis for safety endpoints and summary of investigational product administration will utilize the safety analysis set.

7. Planned Analyses

The primary analysis (or final analysis since there is only one milestone analysis for this study) will occur after all subjects have completed their week-16 visit (or discontinued

from the study). The DBTP treatment assignment will be unblinded and all efficacy and safety analyses will be conducted and reported by the DBTP treatment group.

8. Data Screening and Acceptance

8.1 General Principles

The objective of the data screening is to assess the quantity, quality, and statistical characteristics of the data relative to the requirements of the planned analyses.

8.2 Data Handling and Electronic Transfer of Data

The Amgen Global Study Operations-Data Management (GSO-DM) department will provide all data to be used in the planned analyses. This study will use the RAVE database as well as eDiary data which is outside of the RAVE database.

8.3 Handling of Missing and Incomplete Data

Subjects may miss specific data points for a variety of reasons. In general, data could be missing due to a subject's early withdrawal from the study, a missed visit, or inability to evaluate an endpoint at a time point. For this study, efficacy endpoints will be collected via eDiary and subjects could miss entering several days of data in each monthly interval. The general procedures outlined below describe how missing data will be handled.

For the endpoints derived from the daily diary data, please refer to proration approach specified in Section 5.1.1 on handling missing daily diary data. Missing monthly measurement after proration will be handled by statistical analysis approaches listed in Section 9.5.

For the endpoint derived from the episodic diary data, missing data at timed assessment will be handled by statistical analysis approaches listed in Section 9.5.

Missing items in each clinical outcome assessment questionnaire will be handled based on the scoring algorithm for each assessment. The missing value in the algorithm derived measurements (eg, total score, domain scores) will be handled by statistical analysis approaches listed in Section 9.5.

Missing data in safety endpoints will not be imputed except for incomplete start date of an AE or concomitant medication, which will be imputed as follows:

	Missing	Imputation	Exception on adverse event start date
Start date (AE, concomitant medication)	Day	01	Default to Study Day 1 if an adverse event started the same year and month as Study Day 1 and the flag indicates that the adverse event started on or after the first dose of investigational product on the Events eCRF
	Day/Month	01 JAN	Default to Study Day 1 if an adverse event started the same year as Study Day 1 and the flag indicates that the adverse event started on or after the first dose of investigational product on the Events eCRF
	Day/Month/Year	No imputation	-

8.4 Detection of Bias

This study has been designed to minimize potential bias by allocating treatment groups randomly, assessing endpoints and handling withdrawals without knowledge of the treatment. Other factors that may bias the results of the study include:

- important protocol deviations likely to impact the analysis and interpretation of the efficacy endpoints
- inadvertent breaking of the blind before formal unblinding
- investigational product dosing non-compliance
- the timing of and reasons for early withdrawal from treatment and from study

The incidence of these factors may be assessed. Important protocol deviations will be listed and tabulated. If necessary, the incidence of other factors will be tabulated.

The reasons for early withdrawal from treatment and from study will be tabulated.

8.5 Outliers

Histograms will be examined to identify outliers in any of the continuous variables used in the analyses. Unexpected and/or unexplained values in categorical data will be identified by utilizing frequency tables.

Outliers due to data entry errors will be assessed by the study team before final database lock. The validity of any questionable values or outliers will be confirmed. Outliers or any questionable values with confirmed validity will be included in the analyses. However, ad-hoc sensitivity analyses may be conducted to evaluate the influence of extreme values in the data.

8.6 Distributional Characteristics

Continuous endpoints of change from baseline value will be analyzed under normality assumption. If they deviate appreciably from normality, appropriate transformations or the non-parametric alternatives will be used, such as Quade test (Quade D, 1966) may additionally be considered.

